## Introduction

The chromophore of the 1927 nm diode laser is mainly water, which can be used for skin rejuvenation. This study intends to use the Solta CLEAR+BRILLIANT Laser System, featuring a 1927 nm diode laser with 5 mJ energy, a treatment spot of 140 µm, a treatment depth of 170 µm, and a treatment coverage of approximately 5% per energy level after four rounds of treatment using the patented Intelligent Optical Tracking® System (IOTs). The purpose of this research project is to investigate the treatment design, therapeutic effects and safety of the 1927 nm laser for the rejuvenation of the skin around the eyes.

## Study objectives and endpoints

- **Objectives:** The objective of this study is to evaluate the treatment design, therapeutic effects and safety of the 1927 nm laser for the rejuvenation of the skin around the eyes.
- **Primary endpoint**
  1. Change from baseline in texture score at visit 4 (follow-up session)
- **Secondary endpoints**
  1. Change from baseline in color measurements (L\*) at visit 4 (follow-up session)
  2. Change from baseline in pigmentation score at visit 4 (follow-up session)
  3. Change from baseline in pores' index at visit 4 (follow-up session)
  4. Change from baseline in physician assessment of Global Aesthetic Improvement Score (GAIS), at visit 4 (follow-up session)
  5. Change from baseline in patient assessment of Global Aesthetic Improvement Score (GAIS), at visit 4 (follow-up session)
  6. Change from baseline in texture score at visit 2
  7. Change from baseline in color measurements (L\*) at visit 2
  8. Change from baseline in pigmentation score at visit 2
  9. Change from baseline in pores' index at visit 2
  10. Change from baseline in physician assessment of Global Aesthetic Improvement Score (GAIS), at visit 2
  11. Change from baseline in patient assessment of Global Aesthetic Improvement Score (GAIS), at visit 2
  12. Change from baseline in texture score at visit 3
  13. Change from baseline in color measurements (L\*) at visit 3
  14. Change from baseline in pigmentation score at visit 3
  15. Change from baseline in pores' index at visit 3
  16. Change from baseline in physician assessment of Global Aesthetic

- Improvement Score (GAIS), at visit 3
- 17. Change from baseline in patient assessment of Global Aesthetic Improvement Score (GAIS), at visit 3
- 18. Adverse reaction after each treatment
- 19. Visual Analogue Scale (VAS) during treatment
- 20. Change from baseline in self-reported satisfaction with the skin around the eyes

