## **Investigational plan**

- **Study Design**

This is an open-label, single center clinical study to evaluate the efficacy of periorbital rejuvenation with a 1927 nm diode laser treatment. The trial administrator will assign the subjects into different treatment groups (Group A: 2-week interval between treatments, or Group B: 4-week interval between treatments) .

- **Randomization**

This study is designed as a randomized clinical trial. The randomization of subjects will be generated by computer algorithm prior to the start of the trial. The trial administrator will assign the subjects into different treatment groups (Group A: 2-week interval between treatments, or Group B: 4-week interval between treatments) based on the order of enrollment and the corresponding randomization code.

- **Screening**

Upon obtaining the signed informed consent form, the trial staff will record the subjects' basic information, medical and surgical history, medication history, and Fitzpatrick skin type. Women will undergo pregnancy testing, and inclusion and exclusion criteria will be reviewed.

- **Treatment Visits**

- Visit 1

Before the first treatment, a camera photograph and Antera 3D assessment will be performed, and the subjects will complete a self-assessment questionnaire for skin conditions. EMLA Cream 5% will be applied topically for 20 minutes. Ocular laser shields will then be placed over the eyes following the application of Alcaine Ophthalmic Solution 0.5%. Clear + Brilliant™ Permea device periorbital treatment will then be performed. After the treatment, the subjects will complete a visual analog scale (VAS) for pain and use moisturizing skincare products.

- Visit 2

Before the second treatment, a camera photograph and Antera 3D assessment will be performed, and the subjects will complete a self-assessment questionnaire for skin conditions, the Global Aesthetic Improvement Scale (GAIS) for overall aesthetic improvements, and a treatment safety questionnaire. EMLA Cream 5% will be applied topically for 20 minutes. Ocular laser shields will then be placed over the eyes following the application of Alcaine Ophthalmic Solution 0.5%. Clear + Brilliant™ Permea device periorbital treatment will then be performed. After the treatment, the subjects will use moisturizing skincare products.
- Visit 3

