Before the third treatment, a camera photograph and Antera 3D assessment will be performed, and the subjects will complete a self-assessment questionnaire for skin conditions, GAIS for overall aesthetic improvements, and a treatment safety questionnaire. EMLA Cream 5% will be applied topically for 20 minutes. Ocular laser shields will then be placed over the eyes following the application of Alcaine Ophthalmic Solution 0.5%. Clear + Brilliant™ Permea device periorbital treatment will then be performed. After the treatment, the subjects will use moisturizing skincare products.
- Visit 4

Four weeks after the third treatment, a follow-up assessment will be performed, including a camera photograph and Antera 3D assessment, self-assessment questionnaire for skin conditions, GAIS for overall aesthetic improvements, and a treatment safety questionnaire.
- **Time of Each Visit**

Each visit lasts approximately 40 minutes, including 20-minute topical anesthesia, 15-minute laser treatment, and 5-minute photography.
- **Laser treatment**

Solta CLEAR+BRILLIANT Laser System, featuring a 1927 nm diode laser with 5 mJ energy, a treatment spot of 140 µm, a treatment depth of 170 µm, and a treatment coverage of approximately 5% per energy level after four rounds of treatment using the patented Intelligent Optical Tracking® System (IOTs). We will perform laser treatment on the periorbital area.
- **Imaging Records**

Each visit will include:

  - Camera photograph: One photograph of periorbital area in half-face position (from the eyebrows to the lower nose).

- Antera 3D photography: Two photographs of both sides of the periorbital area (5.6 x 5.6 cm), along with L\*, texture, pigmentation, and pore indices. A total of eight photographs will be taken.
- **Other Study Procedures**
  - Basic information survey, including date of birth, gender, Fitzpatrick skin type, and medication history.
  - Height and weight
  - Medical and surgical history, including a survey of past and current illnesses, allergies, and surgical history.
  - Medication history, concurrent use of medications, or related aesthetic treatments
  - Pregnancy test: urine pregnancy test (only performed on women before menopause).
  - Self-assessment questionnaire for skin condition
  - Global aesthetic improvement scale (GAIS) from subjects and investigator
  - Treatment safety questionnaire
  - Pain VAS (Pain Visual Analogue Scale)
  - Antera 3D camera
 

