Antera 3D® (a product of PSET BioMed and Miravex Limited, Ireland) is a non-invasive inspection tool that uses "image capture" technology to analyze and examine skin. The principle of obtaining the structure of skin texture is based on the colorimetric shape-from-shading (SFS) method, which is widely used to eliminate strong light on the skin and improve the accuracy of the inspection data. With this method, texture reconstruction can be used for skin analysis and quantification, such as measuring wrinkle depth and width, skin damage, and overall roughness. The captured spectral data can also be used to create maps that confirm the distribution and concentration of melanin and hemoglobin. The testing method for subjects involves comparing a fixed area of skin.

	1st treatment (visit 1)	2nd treatment (visit 2)	3rd treatment (visit 3)	Follow-up (visit4)
Group A	Week 0	Week 2	Week 4	Week 8
Group B	Week 0	Week 4	Week 8	Week 12
Camera photograph	V	V	V	V
Pain VAS	V			
Antera 3D assessment	V	V	V	V
Self-assessment questionnaire for skin condition	V	V	V	V
Investigator Global Aesthetic Improvement Scale (GAIS)		V	V	V
Subjects Global Aesthetic Improvement Scale (GAIS)		V	V	V
Treatment safety questionnaire		V	V	V

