## **Adverse Reactions and Management in Clinical Settings**

- Allergic contact dermatitis caused by topical anesthetic cream has an incidence rate of less than 0.1%, which may result in skin redness, swelling, mild burning or itching. Topical steroid cream can be used for treatment.
- This device may cause local transient pain (lasting about one to several

hours) and redness and swelling (lasting about one to two days). Most of these side effects will disappear on their own. If the symptoms persist, symptom relief medication such as oral pain relievers like acetaminophen or non-steroidal anti-inflammatory drugs can be used.

- Small scabs the size of a needle tip may appear, which will fall off on their own within a week.
- If inflammation and pigmentation occur due to the constitution or sun exposure, topical or oral whitening products can be used for treatment for 1-3 months.

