## **Data Collection, Processing, Evaluation, and Statistical Analysis**

### **Methods**

- **Data Confidentiality**

To maintain data confidentiality, data will be entered into a computer using a numbering system, and the data will be stored on an encrypted computer in the lead investigator's institution. The study lead investigator and research team members have a duty of confidentiality regarding information about the subjects and follow the rule that data cannot be taken out of the hospital.

- **Protection of Subjects' Privacy**

The research team will use a study code to represent the identity of the subjects, and only the lead investigator and relevant research team members will know the link between the code and the name. If the trial/research results are published, the subjects' identities will still be kept confidential.

- **Statistical analysis**

- For the analysis of numerical data, we will use either an independent t-test or Mann-Whitney U test to compare differences between the two groups. Additionally, a paired t-test or Wilcoxon signed-rank test will be used to compare differences between before and after treatment.
- For categorical data, we will present the data in the form of frequency and contingency tables. To determine if there are significant differences in rates between the two groups, we will use either the chi-square test or Fisher's exact test.
- All reported P-values will be from two-sided tests, and statistical significance will be determined at a threshold of  $P < 0.05$ .

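### Pain VAS is collected only after the first treatment, before the two intervals diverge, so secondary endpoint 19 carries no information on treatment interval

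*Combined protocol and SAP*

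**What the plan says.** In the combined protocol and SAP, Study objectives and endpoints, secondary endpoint 19 reads "Visual Analogue Scale (VAS) during treatment". It names no visit. The endpoint just before it, number 18, does specify every session: "Adverse reaction after each treatment".

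Under Investigational plan, Randomization, the arms differ in one respect: "Group A: 2-week interval between treatments, or Group B: 4-week interval between treatments".

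Under Treatment Visits, the visit 1 text ends: "After the treatment, the subjects will complete a visual analog scale (VAS) for pain and use moisturizing skincare products". The visit 2 and visit 3 texts repeat the anaesthetic, eye-shield and laser steps, but each ends: "After the treatment, the subjects will use moisturizing skincare products". The schedule table agrees, with pain VAS marked once, in the visit 1 column. The list of other study procedures names the pain VAS without tying it to a visit.

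The schedule also has a row "Treatment safety questionnaire", marked at visits 2, 3 and 4. Its content is not given.

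The statistical analysis section has nothing specific to VAS. Its general rule for numerical data is: "we will use either an independent t-test or Mann-Whitney U test to compare differences between the two groups".

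**The concern.** The objective covers treatment design and safety as well as effect, and interval is the only thing randomised. Whether repeat sessions hurt more at the shorter interval is a natural tolerability question for this trial. The only pain scale is taken at the one session where the two arms have been treated identically.

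Two things follow. First, the general two-group rule, applied to the only VAS available, gives a p-value that a reader could take as evidence about interval when it cannot be. Second, pain at treatments 2 and 3 is never scored by VAS, and ratings not taken on the day cannot be recovered later.

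There is also a small wording gap. The endpoint places the rating in the session, while the visit text has it completed afterwards.

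**Working it through.** The documents give no sample size, VAS mean, VAS SD or power for this endpoint, so there is no stated figure to reproduce. The check sets the schedule against the endpoint and then sizes the consequence.

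**Step 1: coverage.** Timings are from the schedule table.

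| | Visit 1 | Visit 2 | Visit 3 | Visit 4 |
|---|---|---|---|---|
| Group A | Week 0 | Week 2 | Week 4 | Week 8 |
| Group B | Week 0 | Week 4 | Week 8 | Week 12 |
| Laser | yes | yes | yes | no |
| Pain VAS | yes | no | no | no |

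The arms first differ at visit 2. VAS covers 1 of 3 laser sessions and 0 of the 2 after divergence.

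**Step 2: what a visit-1 group test can show.** Treatment up to that point is the same in both arms, so the expected A minus B difference due to interval is 0 whatever the later interval effect. The two-sided 0.05 test then rejects at its null rate:

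- t-test: 5% at any group size (20,000 simulated trials at each of 10, 15, 20 and 30 per group gave 4.7% to 5.0%).
- Exact Mann-Whitney, no ties: 3.2%, 4.3%, 4.5%, 4.9% and 5.0% at 5, 10, 15, 20 and 30 per group.

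The group sizes are assumptions.

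**Step 3: can the safety questionnaire stand in?** It is completed before the next treatment, or at follow-up, so it is retrospective.

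- Treatment 2, recalled at visit 3: Group A, Week 2 to Week 4 = 14 days; Group B, Week 4 to Week 8 = 28 days.
- Treatment 3, recalled at visit 4: Group A, Week 4 to Week 8 = 28 days; Group B, Week 8 to Week 12 = 28 days.

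For treatment 2, recall time is confounded with the randomised interval. For treatment 3 it is equal, but long for pain that the adverse reactions section puts at one to several hours.

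**Step 4: what a VAS at treatment 3 would deliver.** The analysis is ANCOVA on visit-1 VAS, in SD units, with n per group and correlation ρ between the two ratings:

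SE = √(2(1 − ρ²)/n) × √(1 + 1/(2n − 4)), df = 2n − 3.

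For n = 10, ρ = 0.3: SE = √(2 × 0.91/10) × √(1 + 1/16) = 0.427 × 1.031 = 0.440. With t = 2.110 on 17 df, the 95% half-width is 0.928.

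| n per group | ρ | 95% CI half-width (SD) | Power, 0.5 SD | Power, 0.8 SD | Unadjusted t-test power, 0.5 SD |
|---|---|---|---|---|---|
| 10 | 0.3 | 0.928 | 18.9% | 40.4% | 18.5% |
| 20 | 0.5 | 0.563 | 41.9% | 80.1% | 33.8% |
| 30 | 0.7 | 0.373 | 75.2% | 98.8% | 47.8% |

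The group sizes, correlations and effect sizes are assumptions; the documents give none of them.

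**The case against.** The strongest reply is that nothing is broken. Endpoint 18 covers every treatment and endpoint 19 does not say so; text and table consistently place the VAS at the first session. That reads as a deliberate choice to describe first-session pain, which serves the safety objective. No section says the VAS is meant to compare intervals, and the misleading test arises only by applying a general rule. **This stands in part.** It is a gap in design and definition, not a contradiction, and the descriptive use is legitimate. But the protocol does not state that use, and its general rule points to a group comparison.

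Next, there may be little interval effect to find. The adverse reactions section says "This device may cause local transient pain", lasting one to several hours, with redness and swelling for one to two days and pinpoint scabs gone within a week, all shorter than 14 days. The treatment steps are described identically at each session. This is a fair reason to expect a small effect, and the 0.5 and 0.8 SD differences above have no basis in the documents. It does not exclude an effect: the same section also allows for inflammation and pigmentation treated over 1 to 3 months.

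Third, the safety questionnaire follows all three treatments and may ask about pain. It may, but its content is not given, it is retrospective, and recall is unequal for treatment 2.

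Fourth, a small trial would estimate the difference poorly. That is true at 10 per group, which is why the proposal below asks for an estimate and makes no significance claim.

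The timing wording is minor. Rating afterwards the pain felt in the session is the natural reading, particularly with eye shields in place.

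**Conclusion.** The concern holds. As scheduled, endpoint 19 measures pain at 1 of 3 sessions and at none of the 2 sessions where interval could matter. A visit-1 group comparison has no power for an interval effect beyond its false-positive rate of about 5%. That conclusion rests only on the schedule and needs no assumed numbers.

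One caveat: the trial is open-label and the documents do not say when subjects learn their group. Expectation could shift visit-1 ratings, but that would still not be an effect of the interval received.

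The consequence is limited to one secondary tolerability endpoint, but it is cheap to remedy and the sponsor should act on it. The precision available after the change, a half-width of 0.37 to 0.93 SD, depends wholly on the assumed group sizes and correlations.

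**What to change.** 1. Collect the same single-item pain VAS immediately after treatments 2 and 3. Add it to the visit 2 and visit 3 text and mark it in the schedule.
2. Pre-specify the Group A minus Group B difference in VAS at treatment 3, adjusted for visit-1 VAS by ANCOVA, with a 95% CI. Treat treatment 2 as supportive. Report both as estimates without a significance claim, since there are already 20 secondary endpoints and no multiplicity rule.
3. Report visit-1 VAS pooled over groups (mean, SD, median, IQR), with no group inference.
4. Reword endpoint 19 to name the sessions and the moment of rating, so that it matches the visit text.

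If collection is not extended, label endpoint 19 as pain VAS at the first treatment, descriptive only. That prevents misreading but leaves repeat-session pain without a VAS.

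**Cost:** about one minute (an estimate) at each of two existing visits, plus schedule and analysis wording; no extra visits, staff or procedures. The downsides are two more secondary comparisons and limited precision in a small trial, so a null result must be read through its CI and not as absence of a difference.

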## **Investigational plan**

- **Study Design**

This is an open-label, single center clinical study to evaluate the efficacy of periorbital rejuvenation with a 1927 nm diode laser treatment. The trial administrator will assign the subjects into different treatment groups (Group A: 2-week interval between treatments, or Group B: 4-week interval between treatments) .

- **Randomization**

This study is designed as a randomized clinical trial. The randomization of subjects will be generated by computer algorithm prior to the start of the trial. The trial administrator will assign the subjects into different treatment groups (Group A: 2-week interval between treatments, or Group B: 4-week interval between treatments) based on the order of enrollment and the corresponding randomization code.

- **Screening**

Upon obtaining the signed informed consent form, the trial staff will record the subjects' basic information, medical and surgical history, medication history, and Fitzpatrick skin type. Women will undergo pregnancy testing, and inclusion and exclusion criteria will be reviewed.

- **Treatment Visits**

- Visit 1

Before the first treatment, a camera photograph and Antera 3D assessment will be performed, and the subjects will complete a self-assessment questionnaire for skin conditions. EMLA Cream 5% will be applied topically for 20 minutes. Ocular laser shields will then be placed over the eyes following the application of Alcaine Ophthalmic Solution 0.5%. Clear + Brilliant™ Permea device periorbital treatment will then be performed. After the treatment, the subjects will complete a visual analog scale (VAS) for pain and use moisturizing skincare products.

- Visit 2

Before the second treatment, a camera photograph and Antera 3D assessment will be performed, and the subjects will complete a self-assessment questionnaire for skin conditions, the Global Aesthetic Improvement Scale (GAIS) for overall aesthetic improvements, and a treatment safety questionnaire. EMLA Cream 5% will be applied topically for 20 minutes. Ocular laser shields will then be placed over the eyes following the application of Alcaine Ophthalmic Solution 0.5%. Clear + Brilliant™ Permea device periorbital treatment will then be performed. After the treatment, the subjects will use moisturizing skincare products.
- Visit 3

Before the third treatment, a camera photograph and Antera 3D assessment will be performed, and the subjects will complete a self-assessment questionnaire for skin conditions, GAIS for overall aesthetic improvements, and a treatment safety questionnaire. EMLA Cream 5% will be applied topically for 20 minutes. Ocular laser shields will then be placed over the eyes following the application of Alcaine Ophthalmic Solution 0.5%. Clear + Brilliant™ Permea device periorbital treatment will then be performed. After the treatment, the subjects will use moisturizing skincare products.
- Visit 4

Four weeks after the third treatment, a follow-up assessment will be performed, including a camera photograph and Antera 3D assessment, self-assessment questionnaire for skin conditions, GAIS for overall aesthetic improvements, and a treatment safety questionnaire.
- **Time of Each Visit**

Each visit lasts approximately 40 minutes, including 20-minute topical anesthesia, 15-minute laser treatment, and 5-minute photography.
- **Laser treatment**

Solta CLEAR+BRILLIANT Laser System, featuring a 1927 nm diode laser with 5 mJ energy, a treatment spot of 140 µm, a treatment depth of 170 µm, and a treatment coverage of approximately 5% per energy level after four rounds of treatment using the patented Intelligent Optical Tracking® System (IOTs). We will perform laser treatment on the periorbital area.
- **Imaging Records**

Each visit will include:

  - Camera photograph: One photograph of periorbital area in half-face position (from the eyebrows to the lower nose).

- Antera 3D photography: Two photographs of both sides of the periorbital area (5.6 x 5.6 cm), along with L\*, texture, pigmentation, and pore indices. A total of eight photographs will be taken.
- **Other Study Procedures**
  - Basic information survey, including date of birth, gender, Fitzpatrick skin type, and medication history.
  - Height and weight
  - Medical and surgical history, including a survey of past and current illnesses, allergies, and surgical history.
  - Medication history, concurrent use of medications, or related aesthetic treatments
  - Pregnancy test: urine pregnancy test (only performed on women before menopause).
  - Self-assessment questionnaire for skin condition
  - Global aesthetic improvement scale (GAIS) from subjects and investigator
  - Treatment safety questionnaire
  - Pain VAS (Pain Visual Analogue Scale)
  - Antera 3D camera
 

Antera 3D® (a product of PSET BioMed and Miravex Limited, Ireland) is a non-invasive inspection tool that uses "image capture" technology to analyze and examine skin. The principle of obtaining the structure of skin texture is based on the colorimetric shape-from-shading (SFS) method, which is widely used to eliminate strong light on the skin and improve the accuracy of the inspection data. With this method, texture reconstruction can be used for skin analysis and quantification, such as measuring wrinkle depth and width, skin damage, and overall roughness. The captured spectral data can also be used to create maps that confirm the distribution and concentration of melanin and hemoglobin. The testing method for subjects involves comparing a fixed area of skin.

	1st treatment (visit 1)	2nd treatment (visit 2)	3rd treatment (visit 3)	Follow-up (visit4)
Group A	Week 0	Week 2	Week 4	Week 8
Group B	Week 0	Week 4	Week 8	Week 12
Camera photograph	V	V	V	V
Pain VAS	V			
Antera 3D assessment	V	V	V	V
Self-assessment questionnaire for skin condition	V	V	V	V
Investigator Global Aesthetic Improvement Scale (GAIS)		V	V	V
Subjects Global Aesthetic Improvement Scale (GAIS)		V	V	V
Treatment safety questionnaire		V	V	V

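### Nothing in the plan hides group or visit when the measured skin area is matched and the Antera indices are extracted; masked batch extraction would cheaply reduce possible observer bias in the primary endpoint.

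*Combined protocol and SAP*

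**What the plan says.** The Study Design paragraph of the Investigational plan reads "This is an open-label, single center clinical study to evaluate the efficacy of periorbital rejuvenation with a 1927 nm diode laser treatment". Subjects are randomized to a 2-week or a 4-week treatment interval, "based on the order of enrollment and the corresponding randomization code".

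The primary endpoint (Study objectives and endpoints) is the change in texture score from baseline to visit 4. Under Imaging Records, Antera 3D photographs of both periorbital sides, 5.6 x 5.6 cm, are taken at each visit and yield L* and "texture, pigmentation, and pore indices". The same paragraph adds "A total of eight photographs will be taken". The Antera 3D camera description ends with the only statement about the measured region: "The testing method for subjects involves comparing a fixed area of skin".

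Data Confidentiality and Protection of Subjects' Privacy describe a numbering system and study codes. Their stated purpose is confidentiality, and the lead investigator and relevant team members hold the link. No section describes a masked assessor, an independent reader, or images coded by group or visit.

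The Statistical analysis section plans a between-group test (t or Mann-Whitney) and a before-after test (paired t or Wilcoxon), two-sided at 0.05. It does not say which is primary.

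**The concern.** An instrument index depends on the image and the patch of skin it is computed from. Calling the area fixed states an intention. The protocol gives no landmark rule, names no operator and does not say whether that operator knows group and visit. A periorbital frame may include lines, lashes or brow, so a small shift may move the reading.

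If choices at this step lean with knowledge of the visit, the before-after comparison is affected. If they lean with knowledge of the arm, the A-versus-B comparison is affected. The step feeds the primary endpoint and 11 of the 20 secondary endpoints: L*, pigmentation and pores at visit 4 (3), and texture, L*, pigmentation and pores at visits 2 and 3 (4 + 4).

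Subjects and treating staff cannot be masked to a treatment interval. A person extracting indices from saved images can be.

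**Working it through.** **Is there masking anywhere?** Read together, the sections give an open-label design, an area described only as fixed, and codes that serve confidentiality. None of these hides group or visit at extraction.

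**Do the images allow masked reading later?** Two sides x 4 visits = 8 photographs per subject, which matches the stated total. Every visit is imaged, so batch extraction needs no new procedure, provided the images are kept.

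**Would a random file code be enough?** Not if capture dates remain. Visits fall at weeks 0, 2, 4 and 8 in Group A and at weeks 0, 4, 8 and 12 in Group B. Dates therefore reveal both visit order and group.

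**What could a lean do?** The documents give no sample size, SD, effect size or allocation ratio, so there is no planned figure to reproduce. Everything below is illustration. Assumptions: no true effect; equal arms of n = 15, 20 or 30; a systematic lean b of 0.1, 0.2 or 0.3 SD of the change score. From the documents: two-sided alpha of 0.05 and the t-tests.

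*Between groups.* The test statistic follows a noncentral t with 2n − 2 degrees of freedom and noncentrality b·√(n/2). The rejection rate is P(|T| > t at 0.975). For n = 15 and b = 0.3, the noncentrality is 0.3 × √7.5 = 0.822 and the critical value on 28 df is 2.048, which gives 12.5%.

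| n per arm | b = 0 | b = 0.1 | b = 0.2 | b = 0.3 |
|---|---|---|---|---|
| 15 | 5.0% | 5.8% | 8.3% | 12.5% |
| 20 | 5.0% | 6.1% | 9.5% | 15.2% |
| 30 | 5.0% | 6.7% | 11.9% | 20.8% |

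*Before-after within one arm.* Here there are n − 1 degrees of freedom and the noncentrality is b·√n. For n = 15 and b = 0.3 it is 0.3 × √15 = 1.162, the critical value on 14 df is 2.145, and the rate is 19.2%.

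| n in the arm | b = 0 | b = 0.1 | b = 0.2 | b = 0.3 |
|---|---|---|---|---|
| 15 | 5.0% | 6.5% | 11.2% | 19.2% |
| 20 | 5.0% | 7.1% | 13.6% | 24.7% |
| 30 | 5.0% | 8.3% | 18.5% | 35.5% |

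A visit lean that is equal in both arms cancels from the A-versus-B difference but enters the before-after change in full. Both arms receive the laser, so no untreated group would reveal it.

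**The case against.** The strongest reply is that the device computes the index and the area is meant to be fixed. No section describes a reader who draws or places a region. On that view the gap is one of repeatability: imprecise relocation adds noise, and it adds bias only if it also leans with visit or arm. This stands in part. The route for bias is narrower than for the unmasked GAIS, and the operator's role is inferred. It does not close the gap, because the plan neither rules out operator choice nor masks it.

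The assumed size is also open to challenge. No section gives a reason to expect one interval to be favoured, and at 0.1 SD the between-group rate is only 5.8% to 6.7%. That is fair. A lean by visit is the more plausible of the two.

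The Ethical Conduct section refers to an Operations Manual, which might specify positioning and area selection. It was not available to this review, so its possible contents cannot be counted as a safeguard.

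Three stronger readings are tempting and unsupported. A reader might infer that the texture results will be biased, but the documents show only that nothing prevents it. A reader might infer that such bias could never be undone, but if the images are kept, bias from extraction can be corrected by masked re-extraction. Only bias at capture is beyond recovery. Finally, a reader might infer that coded, shuffled files settle the matter, but camera positioning, image selection and retakes at the visit would still be unmasked.

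**Conclusion.** The point holds as a cheap improvement. The trial is open-label, and no section hides group or visit when the area is matched and the indices are extracted. Any operator choice there could bias the primary texture change and the other Antera endpoints.

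The size is unknown. Under an assumed between-arm lean of 0.1 to 0.3 SD, the nominal 5% test becomes 5.8% to 12.5% at 15 per arm and 6.7% to 20.8% at 30 per arm. The same lean by visit gives 6.5% to 19.2% and 8.3% to 35.5% in a within-arm before-after test. These figures rest on assumed arm sizes and an assumed lean; with no lean the rates stay at 5%. The conclusion also takes the texture score to be the Antera texture index, which is the natural reading but is not stated outright.

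**What to change.** 1. Keep all Antera images, and state that the texture score is the Antera texture index.
2. Define the measured area in advance by fixed anatomical landmarks, applied identically to every image. No one then needs to know which image is from visit 1.
3. Export the files under random codes with group, visit and capture date removed.
4. After the last visit 4, extract all indices in one shuffled batch with fixed settings. Use existing staff who do not hold the code list.
5. Lock the index file before joining it to visit and allocation.
6. Write a fixed positioning and retake rule for image capture. State that capture itself remains unmasked, so bias is reduced and not eliminated.

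The cost is a little file handling, and index values are not available until the end. No extra subject, visit, procedure or reader is needed.
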